13.3. Appendix 3: Assessment Windows

13.3.1. Definitions of Assessment Windows for Analyses

Laboratory data, vital signs, ECGs, and genotypic/phenotypic data will be assigned to assessment windows according to actual dates rather than the nominal visit labels as recorded on the eCRF or in the laboratory database.

Prior to visit slotting, assessments are first assigned to a study phase (Screening, Intervention Phase, Extension, or Long Term Follow Up) as defined in Section 13.4.1.

According to the protocol, the nominal target study visit date will be based on the first injection, the Month 1 date. For instance, if Month 1 occurred on July 7th, all subsequent visits are expected to occur on the 7th of each month such that subsequent visits will be August 7th, September 7th, October 7th, etc. Since there are not >28 days in each month of the year, if the Month 1 injection occurred on the 29th, 30th, or 31st of the month, then the target study visit date for the remainder of the visits will be the 28th of the month.

The nominal target study visit day is derived as

- **M1 Target Day** = Date of Actual M1 Injection Visit Date – Date of First Oral lead-in Dose + 1, if subject receives M1 injection; else M1 Target Day = 30.
- **Mx Target Day** = Mx Nominal Target Study Visit Date – Date of First Oral lead-in Dose + 1, for x=2,3, ...

Assessment windows will be derived based on the midpoint between two consecutive planned target study visit dates. For the Snapshot efficacy data, the same approach will be used, except for Month 12, which will use a \pm 6-week window around the projected target study visit date at Month 12.

For parameters which are not scheduled to be assessed at visits, the all-inclusive assessment windows will still be used; however, data summaries will only report scheduled visits. Assessments at unscheduled visits will be included in summaries of worst-case values across visit (e.g. during the intervention phase) and in data listings, as well any algorithms that make use of additional data (e.g., Snapshot).

Table 1 Assessment Windows for Screening, Intervention and Extension Phase Data (Excluding HIV-1 RNA and PK data)

Target (Study Day)	Analysis Window		Analysis Timepoint
	Beginning Timepoint	Ending Timepoint	
Day of earliest record	Assessment Study Day ≤ 1		Screening
For subjects discontinuing prior to receiving first injection:			
30	Assessment Study Day = 2	Study Day of Last CAB/RPV Oral Dose+1	Month 1
	Assessment Study Day > (Study Day of Last CAB/RPV Oral Lead-in Dose +1)		Follow-up
For subjects receiving first injection:			
Day of First Injection	Study Day = 2	$M1 \text{ target day} + \text{floor}[(M2 \text{ target day} - M1 \text{ target day})/2]$	Month 1
M2 Target Day	$M1 \text{ target day} + \text{floor}[(M2 \text{ target day} - M1 \text{ target day})/2] + 1$	$M2 \text{ target day} + \text{floor}[(M4 \text{ target day} - M2 \text{ target day})/2]$	Month 2
M4 Target Day	$M2 \text{ target day} + \text{floor}[(M4 \text{ target day} - M2 \text{ target day})/2] + 1$	$M4 \text{ target day} + \text{floor}[(M6 \text{ target day} - M4 \text{ target day})/2]$	Month 4
M6 Target Day	$M4 \text{ target day} + \text{floor}[(M6 \text{ target day} - M4 \text{ target day})/2] + 1$	$M6 \text{ target day} + \text{floor}[(M9 \text{ target day} - M6 \text{ target day})/2]$	Month 6
M9 Target Day	$M6 \text{ target day} + \text{floor}[(M9 \text{ target day} - M6 \text{ target day})/2] + 1$	$M9 \text{ target day} + \text{floor}[(M12 \text{ target day} - M9 \text{ target day})/2]$	Month 9
M12 Target Day	$M9 \text{ target day} + \text{floor}[(M12 \text{ target day} - M9 \text{ target day})/2] + 1$	$M12 \text{ target day} + \text{floor}[(M15 \text{ target day} - M12 \text{ target day})/2]$	Month 12
M15 Target Day	$M12 \text{ target day} + \text{floor}[(M15 \text{ target day} - M12 \text{ target day})/2] + 1$	$M15 \text{ target day} + \text{floor}[(M18 \text{ target day} - M15 \text{ target day})/2]$	Month 15
M18 Target Day	$M15 \text{ target day} + \text{floor}[(M18 \text{ target day} - M15 \text{ target day})/2] + 1$	$M18 \text{ target day} + \text{floor}[(M21 \text{ target day} - M18 \text{ target day})/2]$	Month 18
M x Target Day	$M(x-3) \text{ target day} - \text{floor}[(Mx \text{ target day} - M(x-3) \text{ target day})/2] + 1$	$Mx \text{ target day} + \text{floor}[(M(x+3) \text{ target day} - Mx \text{ target day})/2]$	Month x For $x = 21, 24, \text{ etc.}$

Target (Study Day)	Analysis Window		Analysis Timepoint
	Beginning Timepoint	Ending Timepoint	
For subjects who permanently discontinue study treatment:			
	Assessment Study Day > Max (Study Day of Last Dose of Oral Study Treatment (CAB+RPV or SOC Bridging) + 1, Study Day of Last CAB + RPV Injection + 35)		Follow-up

Table 2 Assessment Windows for Screening and Intervention Phase HIV-1 RNA Data

Target (Study Day)	Analysis Window		Analysis Timepoint
	Beginning Timepoint	Ending Timepoint	
Day of earliest record	Assessment Study Day \leq 1		Screening
	For subjects discontinuing prior to receiving first injection:		
28	Assessment Study Day = 2	Study Day of Last Oral Lead-in Dose +1	Month 1
	Assessment Study Day > (Study Day of Last CAB/RPV Oral Lead-in Dose +1)		Follow-up
	For subjects receiving first injection:		
Date of First Injection	Study Day = 2	M1 target day + $\text{floor}[(M2 \text{ target day} - M1 \text{ target day})/2]$	Month 1
M2 Target Day	M1 target day + $\text{floor}[(M2 \text{ target day} - M1 \text{ target day})/2]$ +1	M2 target day + $\text{floor}[(M4 \text{ target day} - M2 \text{ target day})/2]$	Month 2
M4 Target Day	M2 target day + $\text{floor}[(M4 \text{ target day} - M2 \text{ target day})/2]$ +1	M4 target day + $\text{floor}[(M6 \text{ target day} - M4 \text{ target day})/2]$	Month 4
M6 Target Day	M4 target day + $\text{floor}[(M6 \text{ target day} - M4 \text{ target day})/2]$ +1	M6 target day + $\text{floor}[(M8 \text{ target day} - M6 \text{ target day})/2]$	Month 6
M8 Target Day	M6 target day + $\text{floor}[(M8 \text{ target day} - M6 \text{ target day})/2]$ +1	M8 target day + $\text{floor}[(M10 \text{ target day} - M8 \text{ target day})/2]$	Month 8
M10 Target Day	M8 target day + $\text{floor}[(M10 \text{ target day} - M8 \text{ target day})/2]$ +1	M12 target day - 43	Month 10
M12 Target Day	M12 target day - 42	M12 target day + 42	Month 12
M13 Target Day	Assessment Study Day > M12 target day + 42		Month 13

Target (Study Day)	Analysis Window		Analysis Timepoint
	Beginning Timepoint	Ending Timepoint	
For subjects who permanently discontinue study treatment during the Intervention Phase:			
	Assessment Study Day > Max (Study Day of Last Dose of Oral Study Treatment (CAB+RPV or SOC Bridging) +1, Study Day of Last CAB + RPV Injection + 35)		Follow-up

Table 3 Assessment Windows for Extension Phase HIV-1 RNA Data

Target (Study Day)	Analysis Window		Analysis Timepoint
	Beginning Timepoint	Ending Timepoint	
M13 Target Day	Study Day of Nominal Month 13 Visit	M13 target day + floor [(M15 target day – M13 target day)/2]	Month 13
M15 Target Day	M13 target day + floor [(M15 target day – M13 target day)/2] + 1	M15 target day + floor [(M16 target day – M15 target day)/2]	Month 15
M16 Target Day	M15 target day + floor [(M16 target day – M15 target day)/2] + 1	M16 target day + floor [(M18 target day – M16 target day)/2]	Month 16
M18 Target Day	M16 target day + floor [(M18 target day – M16 target day)/2] + 1	M18 target day + floor [(M19 target day – M18 target day)/2]	Month 18
M _x Target Day	M(_{x-1}) target day + floor [(M _x target day – M(_{x-1}) target day)/2] + 1	M _x target day + floor [(M(_{x+2}) target day – M _x target day)/2]	Month _x For _x =19, 22, 25, 28 etc.
M _x Target Day	M(_{x-2}) target day + floor [(M _x target day – M(_{x-2}) target day)/2] + 1	M _x target day + floor [(M(_{x+1}) target day – M _x target day)/2]	Month _x For _x =21, 24, 27, 30 etc.
For subjects who permanently discontinue study treatment during the Extension Phase:			
	Assessment Study Day > Max (Study Day of Last Dose of Oral Study Treatment (CAB+RPV or SOC Bridging) +1, Study Day of Last CAB + RPV Injection + 35)		Follow-up

Table 4 Assessment Windows for Study Visit Length Data (Intervention and Extension Phase)

Target (Study Day)	Analysis Window		Analysis Timepoint
	Beginning Timepoint	Ending Timepoint	
Study Day of Actual M1 Injection	Study Day of Actual M1 Injection		Month 1
Study Day of Actual M5 Injection	Study Day of Actual M5 Injection		Month 5
Study Day of Actual M11 Injection	Study Day of Actual M11 Injection		Month 11
Study Day of Actual M14 Injection	Study Day of Actual M14 Injection		Month 14
Study Day of Actual M x Injection	Study Day of Actual M x Injection		Month x For $x=17, 20,$ etc.
	If none of the above, then Analysis Timepoint = Other		

Table 5 Assessment Windows for Summaries of Long-Term Follow-up Phase Data from Subjects who Received at Least One Injection of CAB+RPV and Permanently Discontinued from the Study

Day of Assessment	Assessment Window	Target LTFU Study Day of Window
1 ≤ LTFU Study Day ≤ 135	LTFU Month 3	90
136 ≤ LTFU Study Day ≤ 225	LTFU Month 6	180
226 ≤ LTFU Study Day ≤ 315	LTFU Month 9	270
316 ≤ LTFU Study Day ≤ 405	LTFU Month 12	360
(30*m-44) ≤ LTFU Study Day ≤ (30*m+45)	LTFU Month m M = 15, 18, 21	30*m

- LTFU Study Day is defined in 13.6.1

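### A minus sign in Table 1 opens the Month 21, 24, … windows about 90 days too early, so each overlaps nearly all of the previous visit's window

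*SAP*

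**What the plan says.** Section 13.3.1 states the principle: "Assessment windows will be derived based on the midpoint between two consecutive planned target study visit dates". Targets fall on the same calendar day each month, because "the nominal target study visit date will be based on the first injection, the Month 1 date".

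The table concerned is "Table 1 Assessment Windows for Screening, Intervention and Extension Phase Data (Excluding HIV-1 RNA and PK data"). Its Month 18 row starts at "M15 \text{ target day} + \text{floor}[(M18 \text{ target day} - M15 \text{ target day})/2] + 1" and ends at "M18 \text{ target day} + \text{floor}[(M21 \text{ target day} - M18 \text{ target day})/2"]. The generic row for Month x (x = 21, 24, etc.) starts at "M(x-3) \text{ target day} - \text{floor}[(Mx \text{ target day} - M(x-3) \text{ target day})/2] + 1"; the sign at issue is the minus in "M(x-3) \text{ target day} - \text{floor}[(Mx".

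Section 13.6.1 adds that, when a window holds more than one value, the one nearest the target day is used, and values at equal distance are averaged. Section 13.3.1 has no rule for a record that falls inside two windows. The top-down sequential rule in section 13.4.1 concerns study phases, not visit windows.

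**The concern.** The generic row contradicts the midpoint principle, the sign used in the rows from Month 2 to Month 18, and the end of the Month 18 row. That row stops at the Month 18/Month 21 midpoint, so Month 21 should begin the next day. Instead it begins before the Month 18 target.

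At stake are the by-visit rows at Month 21 and later in the end-of-study displays: CD4+ (Tables 2.8, 2.9), chemistry (3.26, 3.27), haematology (3.30, 3.31) and vital signs (3.37). Participants stay on study only until commercial supply is available (Schedule of Activities, section 13.2.1.1), so departures between extension visits are expected. Someone who leaves after Month 18, or misses Month 21, has no later value to displace the Month 18 one. The Follow-up row does not prevent this: it removes only assessments made after treatment has lapsed, and a Month 18 value taken on treatment stays eligible.

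**Working it through.** **Notation.** T(x) is the target day of Month x, and h = floor[(T(x) − T(x−3))/2].

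- Start as printed: T(x−3) − h + 1
- Start by the midpoint rule: T(x−3) + h + 1
- End, the same in both: T(x) + floor[(T(x+3) − T(x))/2]

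**Size of the shift.** The two starts differ by 2h. Three calendar months span 89 to 92 days, so h is 44, 45, 45 or 46 and the shift is 88, 90, 90 or 92 days.

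**Example.** Section 13.3.1 illustrates with Month 1 on 7 July. The year (2019) and the oral start (7 June) are assumed. Targets are T(15) = 459, T(18) = 550, T(21) = 640, T(24) = 732 and T(27) = 824.

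| Window | Start | End | Length (days) |
|---|---|---|---|
| Month 18 | 459 + 45 + 1 = 505 | 550 + 45 = 595 | 91 |
| Month 21, printed | 550 − 45 + 1 = 506 | 640 + 46 = 686 | 181 |
| Month 21, midpoint | 550 + 45 + 1 = 596 | 686 | 91 |
| Month 24, printed | 640 − 46 + 1 = 595 | 732 + 46 = 778 | 184 |
| Month 24, midpoint | 640 + 46 + 1 = 687 | 778 | 92 |

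The printed Month 21 window shares days 506 to 595 with Month 18. That is 90 of the 91 Month 18 days, including the Month 18 target (day 550). The printed Month 24 window contains the whole of the intended Month 21 window (596 to 686).

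**Sensitivity to dates.** The calculation was repeated for every Month 1 date in the 730 days from 1 July 2019, with oral lead-ins of 28, 30 and 35 days (assumed ranges). For both Month 21 and Month 24:

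- the shift is 88 to 92 days;
- the printed window is 179 to 184 days long, against 90 to 92 by the midpoint rule;
- the overlap covers 88 to 92 days of the previous visit's 90-to-92-day window (97.8% to 100%) and always includes its target;
- with a plus sign, each window starts the day after the preceding one ends.

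**Who can be misreported.** In the example, a Month 18 value on day 550 lies 640 − 550 = 90 days from the Month 21 target. A record inside the intended Month 21 window lies at most 686 − 640 = 46 days away and so wins under section 13.6.1. The nearest day in the overlap, 595, is 45 days away, so it could tie with or beat only a record on day 685 or 686. In practice, carry-over is confined to participants with no record in the intended window.

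**Whether the minus comes from the PDF.** The same minus appears in Table 1 of the pre-amendment RAP reproduced in the same file. That RAP also had minus signs in the Table 3 extension rows for HIV-1 RNA. RAP Amendment 1 changed those to plus and left Table 1 as it was. The error is in the plan.

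**The case against.** The strongest reply is that this is an obvious typographical slip. The midpoint sentence, the preceding rows and the end of the Month 18 row all show the intended formula, and a programmer would probably follow them. The reach is also limited: no hypothesis is tested (section 2.4), the primary analysis is in a separate plan (section 7), and only descriptive rows at Month 21 and later are involved. All of that limits the importance. It does not make the rule right: followed exactly, it gives wrong windows, and the amendment that corrected the companion table did not correct this one.

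Three stronger conclusions might be inferred, and the SAP does not support them.

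- *All summaries at Month 21 and later are wrong.* The nearest-to-target rule protects participants with a genuine record there. HIV-1 RNA has its own windows, and neither the Month 12 Snapshot nor worst-case summaries across visits depend on this row.
- *Month 18 values are certain to be reported twice.* That requires one record to receive two analysis timepoints, which the SAP neither allows nor forbids. A program that assigns each record once, to the first matching row or the nearer target, would leave an on-target Month 18 value at Month 18. One that takes the last match could move it to Month 21. What is established is an ambiguity that permits misreporting.
- *ECG summaries are distorted.* Appendix 13 plans only ECG listings (43 and 44), with no by-visit ECG table.

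**Conclusion.** The point stands, with limited reach. The Table 1 start for Month 21, 24 and later has the wrong sign. The window opens 88 to 92 days early, is about twice its proper length, and overlaps at least 97.8% of the preceding window over the dates examined, with no stated rule for records in the overlap. The previous visit's value can be summarised at Month 21 or later for participants who lack a nearer record, which would inflate n in the end-of-study tables named above.

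The day counts in the example rest on the assumed 2019 start; the 88-to-92-day range needs only the calendar. The effect on reported n and means cannot be sized, because the SAP does not say how many participants reach Month 21 or lack a record there. It is a definite error in secondary descriptive displays and should be corrected before the end-of-study tables are run.

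**What to change.** In Table 1, row Month x (x = 21, 24, etc.), set the beginning timepoint to M(x−3) target day + floor[(Mx target day − M(x−3) target day)/2] + 1, in line with the Month 15 and Month 18 rows. Confirm that the slotting program uses the plus sign. This restores contiguous windows of 90 to 92 days, so no separate overlap rule is needed for these rows. The cost is one character in the SAP and a check of one line of code; no data collection changes.

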See footnote "c" for continuation of visit schedule after Month 12, if required. Subjects will continue on study until the CAB + RPV LA regimen is either locally approved and commercially available, the participant no longer derives clinical benefit or meets a protocol-defined reason for discontinuation or until development is terminated.

- a. A screening visit will be conducted within 21 days of Day 1. However, it is preferred for Day 1 to be conducted as soon as practical after all screening results are available.
- b. After discussion of risk:benefit, a pregnancy specific ICF addendum must be signed by pregnant participants who wish to remain in the study
- c. Continue this pattern for visits for the remainder of the study if needed, until commercial CAB + RPV LA is available. For example, Month 13 will be conducted as per Month 10, Month 14 will be conducted as per Month 11, Month 15 will be conducted as per Month 12, Month 16 will be conducted as per Month 10, and so on. The exception to this pattern is that no questionnaires, study visit length collection, or patient interviews will be conducted after the Month 12 visit.
- d. Physical exams should be conducted as part of normal routine clinical care but data will not be collected in the electronic case report form (eCRF). Medical assessments include any decisions the study staff must make for participant management.
- e. Measure vital signs after about 5 minutes of rest in a semi-supine position.

- f. Height collected at Day 1 only.
- g. At Screening, ECGs should be performed in triplicate at least 5 minutes apart and following 5 minutes of rest in a semi-supine position. ECG evaluations performed at subsequent visits should be obtained after dosing, preferably 2-4 hours post dosing. ECG at Withdrawal should be performed following 5 minutes of rest in a semi-supine position.
- h. A (-) urine pregnancy test is required prior to any injection and as required by medical monitor after a treatment interruption. A (+) urine test should be confirmed with a stat serum test. A Serum pregnancy test should be performed at any time pregnancy is suspected by the Investigator and may be used in place of a urine test at the discretion of the investigator. Pregnant participants who remain in the study do not need pregnancy testing during the study, for the duration of their pregnancy. Pregnant participants remaining in the study have additional assessments required, as described in [Appendix 8](#).

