13.4. Appendix 4: Study Phases and Treatment Emergent Adverse Events

13.4.1. Study Phases

AEs will be assigned to study phases as defined in Table 6. Laboratory data (efficacy, safety, and virology), HIV associated Conditions, health outcomes assessments, vital signs, and ECGs will be assigned to study phases as defined in Table 7.

Assessments/events are assigned to study phases sequentially, starting from the top of each table.

Table 6 Study Phases for AEs

Study Phase	Definition
Screen	Date < Intervention Phase Treatment Start Date
Intervention	
For subjects continuing into the Extension Phase: Intervention Phase Treatment Start Date \leq Date < Date of Nominal Month 13 Visit
 
For subjects not continuing into the Extension Phase: Intervention Phase Treatment Start Date \leq Date < LTFU ART Start Date [a]
 
For AEs leading to treatment withdrawal with start date equal to the LTFU ART Start Date, Intervention Phase instead of Long-term Follow-up Phase will be assigned.

Extension Phase	
Date of Nominal Month 13 Visit \leq Date < LTFU ART Start Date [a]
 
For AEs leading to treatment withdrawal with start date equal to the LTFU ART Start Date, Extension Phase instead of Long-Term Follow-up Phase will be assigned.

Long Term Follow-Up	
For subjects who receive at least one CAB/RPV injection and permanently discontinue study treatment: AE Start Date \geq LTFU ART Start Date
 
AEs with completely missing start date:
 
 • If AE end date is \leq Intervention Phase Treatment Start Date, then assign to Screening Phase; • Else if AE end date is completely missing or Intervention Phase Treatment Start Date $<$ AE end date \leq Date of Nominal Month 13 Visit, then assign to Intervention Phase; • Else if AE end date $>$ Date of Nominal Month 13 Visit, then assign to Extension Phase.

Date=AE Start Date

- [a] If participants have missing LFTU ART start date, only the lower bound will be considered in the derivation.

Table 7 Study Phases for Laboratory, PK, ECG, Vital Signs, HIV-1 Associated Conditions, and Protocol Deviation Data

Study Phase	Definition
Screen	Date ≤ Study Treatment Start Date
Intervention	
For subjects continuing into the Extension Phase: Intervention Phase Treatment Start Date < Date < Date of Nominal Month 13 Visit
 
For subjects not continuing into the Extension Phase: Intervention Phase Treatment Start Date < Date ≤ LTFU ART Start Date ^[a]

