Extension Phase	For subjects continuing into Extension Phase: Date of Nominal Month 13 Visit ≤ Date ≤ LTFU ART Start Date ^[a]
Long Term Follow-Up	For subjects who receive at least one CAB/RPV injection and permanently discontinue study treatment: Assessment Date > LTFU ART Start Date

- Date = start or assessment date
- [a] If participants have missing LFTU ART start date, only the lower bound will be considered in the derivation.

Study phase of discontinuation will be determined according to Table 8.

Table 8 Study Phases for Study Conclusion/IP Discontinuation

Study Phase	Definition
Intervention Phase	
For IP Discontinuation: Discontinuation Date is not missing, and no assessments collected at any extension phase nominal visits (e.g. Month 13, Month 15, Month 17 etc.).
 
For Study Conclusion: Discontinuation or Completion Date is not missing, and no assessments collected at any extension phase nominal visits (e.g. Month 13, Month 15, Month 17 etc.) and at any LTFU phase nominal visits (e.g. LTFU Month 3, LTFU Month 6, etc.)

Extension Phase	
For IP Discontinuation: Discontinuation Date is not missing, and assessments collected at any extension phase nominal visits (e.g. Month 13, Month 15, Month 17 etc.).
 
For Study Conclusion: Discontinuation or Completion Date is not missing, and assessments collected at any extension phase nominal visits (e.g. Month 13, Month 15, Month 17 etc.) but no assessments collected at any LTFU phase nominal visits (e.g. LTFU Month 3, LTFU Month 6, etc.)

LTFU Phase	
Not applicable for IP Discontinuation.
 
For Study Conclusion: Discontinuation or Completion Date is not missing, and assessments collected at any LTFU phase nominal visits or has taken any LTFU ART medications (e.g. LTFU Month 3, LTFU Month 6, etc.)

- Discontinuation or Completion Date = date of failure to complete study/date of completing study/date of IP discontinuation

Medication use will be classified as prior and concomitant with study treatment according to Table 9, noting that a medication can be assigned as “taken” during more than one study phase.

Table 9 Study Phases for Non-ART Medications/ART Medications

	Definition
Prior	Medication Taken < Intervention Treatment Start Date

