13.6. Appendix 6: Derived and Transformed Data

13.6.1. General

Multiple Measurements at One Analysis Time Point

 If there are two values within a time window (as per Section 13.3.1) the value closest to the target day for that window will be used. If values are the same distance from the target, then the mean (geometric mean for HIV-1 RNA, arithmetic mean for all other measurement) will be taken. Assessments not chosen for use in summary statistics by this algorithm will still appear in the associated listings. All applicable valid assessments, irrespective of proximity to the target study day, will be used when categorizing values across visits, such as 'maximum grade during the intervention phase' or 'at any time post-baseline', and for any algorithm that has specific rules for which observation to use (e.g. snapshot algorithm, LOCF or CVF identification). Participants having both High and Low values for Normal Ranges at any post-baseline visit for safety parameters will be counted in both the High and Low categories of "Any visit post-baseline" row of related summary tables. This will also be applicable to relevant Potential Clinical Importance summary tables.
Treatment Start Date

 Intervention Phase Treatment Start Date = Earliest date of CAB + RPV oral lead-in entered in the IP exposure eCRF form
Nominal Month 13 Visit Date

 For participants who received Month 13 injection, the nominal Month 13 visit date is defined by the Month 13 injection date. Otherwise, nominal Month 13 visit date is defined by the date of latest Month 13 assessment. For participants who continued into Extension Phase but missed the Month 13 visit, the nominal Month 13 visit date is defined by the last contact date prior to the date of the first nominal extension phase visit (e.g. Month 15, Month 17, etc.).
Study Day

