13.6.3. Efficacy

Efficacy	
Snapshot	

 • The Snapshot algorithm is intended to be primarily a virologic assessment of the endpoint, and as such follows a "virology first" hierarchy. • 'HIV-1 RNA < 50 c/mL' or 'HIV-1 RNA ≥ 50 c/mL' within an analysis window (see Table 2 and Table 3) is typically determined by the last available HIV-1 RNA measurement in that window while the participant is On-treatment in the Intervention Phase (as assigned based on Section 13.3). • When no HIV-1 RNA data is available within a window, a participant cannot be assigned to the category of 'HIV-1 RNA < 50 c/mL'. Depending on the reason for lack of data, the participant will be classified as 'HIV-1 RNA ≥ 50 c/mL' or reported as 'No Virologic Data at Week X'; in the latter case, the algorithm further classifies the nature of the missing data. Typically, a participant withdrawn (i) due to AE or, (ii) for another reason yet was suppressed at the time, will be counted as 'No Virologic Data at Week X'. Should a participant withdraw for reasons other than AE and was not suppressed at the time, they will be categorized as 'HIV-1 RNA ≥ 50 c/mL'. 	

Efficacy

 Full details of the algorithm, including the handling of special cases, are included in Appendix 9: Snapshot Algorithm Details.
Plasma HIV-1 RNA

 For summaries and analyses which use HIV-1 RNA level as a continuous measure, the logarithm to base 10 of the value will be used. HIV-1 RNA results may be provided as censored values, such as <40 or >9,999,999 c/mL. For the purposes of summary statistics, such values will be replaced by the next value beyond the limit of detection, e.g., 39 or 10,000,000 c/mL, respectively, for the given examples. Data listings will show the censored values as provided.
Confirmed Virologic Failure (CVF)

 For the purposes of clinical management in this study, CVF is defined as: 
 Rebound as indicated by two consecutive plasma HIV-1 RNA levels \geq 200 c/mL. The CVF definition is provided in the protocol Section 7.1.3 Only plasma HIV-1 RNA values determined by the central laboratory will be used to assess virologic failure.
CDC Classification for HIV-1 Infection (2014)

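### For participants who continue and attend Month 13 on schedule, phase assignment ends the Month 12 Snapshot window at +20 to +37 days instead of the stated +42, so an observed in-window viral load can be set aside as missing or replaced by an older value

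*SAP*

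**What the plan says.** **Window.** SAP 13.3.1 derives windows from midpoints between target visits, "except for Month 12, which will use a \pm 6-week window around the projected target study visit date at Month 12". Table 2 codes this as "M12 target day - 42" through 42 days after target. It places Month 13 only beyond that upper bound.

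**Order of operations.** The same section states: "Prior to visit slotting, assessments are first assigned to a study phase".

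**Phase boundary.** For laboratory data of participants who continue, Table 7 in 13.4.1 defines the Intervention Phase as "Intervention Phase Treatment Start Date < Date < Date of Nominal Month 13 Visit" and the Extension Phase as "Date of Nominal Month 13 Visit ≤ Date ≤ LTFU ART Start Date". Section 13.6.1 fixes the boundary date: "For participants who received Month 13 injection, the nominal Month 13 visit date is defined by the Month 13 injection date".

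**Data that Snapshot may use.** Under 13.6.3 the outcome "is typically determined by the last available HIV-1 RNA measurement in that window while the participant is On-treatment in the Intervention Phase". By contrast, 7.1.3 and Appendix 9 step 3.1 take the last on-treatment value within the window and do not mention phase.

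**Schedule.** Footnote c of the schedule of activities says "Month 13 will be conducted as per Month 10". HIV-1 RNA is marked at Month 10 and Month 12 but not at Month 11, so a viral load is planned at Month 13.

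**No eligible value.** Appendix 9 step 3.2.1 puts a participant still on study into the no-virologic-data category, as on study with data missing from the window. Where the reason is COVID-19, 13.7.2.2 carries forward the last on-treatment value from an earlier timepoint.

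**The concern.** The declared window and the phase rule do not describe the same set of eligible measurements. A reader of 13.3.1, 7.1.3 or Appendix 9 would expect any on-treatment viral load up to day +42 to count. A programmer following Table 7 and 13.6.3 would drop the Month 13 result, because it belongs to the Extension Phase before slotting begins. Two programmers could classify the same participant differently.

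The case that matters is a participant who missed the Month 12 draw, stayed on treatment and was measured at Month 13. The window was widened to six weeks, yet the next scheduled measurement after Month 12 is the one the phase rule removes. Display Table 2.2 then reports no data. Display Table 2.1 may report a value taken about two months before target in preference to one taken about one month after it.

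**Working it through.** **Inputs**
- Window: 6 × 7 = 42 days each side (13.3.1), which reproduces the Table 2 bounds. Inclusive width: 2 × 42 + 1 = 85 days.
- Target dates: same calendar day each month, or the 28th if the first injection fell on the 29th to 31st (13.3.1).
- Visit allowance from Month 4 onward: ±7 days (schedule footnote k).
- Planned patients: 115 (2.3).

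**Step 1: gap from Month 12 to Month 13.** Applying the target-date rule to every first-injection date in 2019–2020 (an assumed calendar range) gives gaps of 28, 29, 30 or 31 days.

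**Step 2: last usable day.** For gap *g* and visit offset *o*, Month 13 falls at *g + o* days after the Month 12 target. Table 7 uses a strict inequality, so the last Intervention Phase day is *g + o − 1*. The usable width is 42 + 1 + (*g + o − 1*).

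| Gap *g* | Month 13 visit at *o* = −7 / 0 / +7 | Last usable day | Usable days out of 85 |
|---|---|---|---|
| 28 | +21 / +28 / +35 | +20 / +27 / +34 | 63 / 70 / 77 |
| 29 | +22 / +29 / +36 | +21 / +28 / +35 | 64 / 71 / 78 |
| 30 | +23 / +30 / +37 | +22 / +29 / +36 | 65 / 72 / 79 |
| 31 | +24 / +31 / +38 | +23 / +30 / +37 | 66 / 73 / 80 |

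Every Month 13 visit within its allowance lies inside +42 and is excluded. The loss is 12 to 15 days for visits on target and 5 to 22 days over the whole allowance.

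**Step 3: is another scheduled value eligible?** The Month 10 target is 59 to 62 days before the Month 12 target. Even a Month 10 visit 7 days late is at −59 + 7 = −52, outside −42. Month 11 has no scheduled viral load. A participant on schedule who misses the Month 12 draw therefore has no other scheduled eligible value, and COVID-19 carry-forward would normally take Month 10.

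**Step 4: when the cut stops mattering.** Month 13 falls beyond +42 only if it is late by more than 42 − 31 = 11 to 42 − 28 = 14 days, depending on the gap.

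**Step 5: size per participant.** 1/115 = 0.87 percentage points, taking the planned number as denominator.

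**Step 6: direction.** In display Table 2.2, an ignored value below 50 c/mL understates the <50 proportion, and an ignored value of 50 or more understates the ≥50 proportion. In display Table 2.1, the result changes only if the carried-forward value and the Month 13 value lie on opposite sides of 50.

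**The case against.** The strongest reply is that the phase limit is deliberate and visible. Table 2 is titled for Screening and Intervention Phase data, Appendix 9 points to Table 2 for its windows, display Tables 2.1 to 2.5 carry the Intervention Phase label, and Table 3 gives Month 13 its own slot. On that reading, +42 is an outer bound within a phase. This stands as far as it goes: the limit is not hidden, and an Intervention Phase outcome is defensible. It does not settle the matter, because 13.3.1 states the six-week window without qualification, 7.1.3 has no phase limit, 13.6.3 hedges its limit as typical while citing Table 3 as well as Table 2, and no reason for the cut is given in a study with one treatment group.

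The second reply concerns scope, and it is right. A reader might infer that the upper half of the window is never fully available. The documents do not support that:
- Participants who do not continue are cut at the start of follow-up therapy, not at Month 13.
- The adherence categories in 13.6.2 provide for injections more than 14 days late, which can put Month 13 beyond +42.
- For a continuer who missed Month 13, the boundary is the last contact before the first extension visit, which may also fall after +42.
- Without a Month 13 injection, the boundary is the latest Month 13 assessment, so an earlier-dated Month 13 sample still counts.
- Late, repeat or unscheduled draws before the Month 13 visit remain eligible.

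Third, the outcome is secondary and descriptive. The viral loads appear in Listing 9, Listing 10 shows outcomes with and without imputation, and display Table 2.12 gives an observed-case summary at end of study. This limits the harm but does not correct the Month 12 classification.

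**Conclusion.** The conflict is real and should be resolved. For participants who continue and attend Month 13 within ±7 days, the usable Month 12 window ends at +20 to +37 days instead of +42. Misclassification as missing, or replacement by an older value, needs three things together: no on-treatment value from −42 up to the Month 13 visit, continuation into the Extension Phase, and an on-treatment Month 13 value by +42. Carry-forward further needs a COVID-19-related miss. Where an earlier eligible value exists, that value is used, and the later in-window Month 13 value is still ignored.

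A reader might also infer a downward bias in the <50 proportion. The documents do not support a fixed direction, since it depends on the ignored result. Nor do they allow the number affected to be derived; only the 0.87 points per participant is firm, and only for a denominator of 115.

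**What to change.** Reconcile 13.3.1 with Table 2, 13.6.3 and Appendix 9. State that, for the Month 12 Snapshot, an on-treatment HIV-1 RNA value on or before 42 days after the Month 12 target is eligible whatever its phase, at minimum before a participant is called missing or COVID-19 carry-forward is applied.

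State also whether the last-value rule extends to Extension Phase values when an Intervention Phase value exists. A fallback used only when Month 12 is missing would leave a participant below 50 at Month 12 and at 50 or more at an in-window Month 13 classified as below 50, so it would not by itself restore the last-value rule of 7.1.3. Footnote how many participants were classified by an Extension Phase value.

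The cost is a sentence or two and minor programming. One value may then serve both the Month 12 Snapshot and the Month 13 summary. If Month 12 output has already been produced, as the end-of-study notes in Appendix 13 suggest without proving, keep the reported analysis and add this as a labelled sensitivity analysis.
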